### 8.1 Rollover Subjects

### 8.1.1 Inclusion Criteria

- 1. Subject's legally appointed and authorized representative (e.g., parent or legal guardian) will sign and date an informed consent form (ICF).
- 2. Completed the 24-week Treatment Period and the Safety Follow-up Visit in Study 122B.

Note: Subjects who had study drug interruptions during Study 122B are eligible for Study 124 if they completed the study visits in the Treatment Period and the Safety Follow-up Visit. Subjects who had a study drug interruption at Week 24 of Study 122B or subjects who resumed study drug in Study 122B after a study drug interruption due to elevated transaminases but who did not complete at least 4 weeks of rechallenge with study drug (due

- to <4 weeks remaining in the Study 122B Treatment Period) must meet eligibility criteria and receive approval from the Vertex medical monitor.
- 3. Subject's legally appointed and authorized representative (e.g., parent or legal guardian) are willing to have the subject remain on a stable CF medication regimen through the Safety Follow-up Visit.

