#### 12.3.5.1 Adverse Events

AEs will be classified as pretreatment AEs or treatment-emergent adverse events (TEAEs), defined as follows:

Pretreatment AE: Any AE that started before the first dose date of study drug in Study 124

**TEAE:** Any AE that worsened (either in severity or seriousness) or that was newly developed on or after the first dose date of study drug through the end of the TE Period of the Current Study Period

**Post-treatment AE**: Any AE that increased in severity or that newly developed after the TE Period of the Current Study Period

For AEs with missing or partial start dates, if there is no clear evidence that the AEs started before or after study treatment, the AEs will be classified as TEAEs.

Details for imputing missing or partial start dates of AEs will be described in the SAP.

TEAE summaries will be presented using number and percentages of subjects for the Current Study Period based on the 124 Safety Set overall.

An overview of the TEAE profile will be provided, including total number of TEAEs, with number and percentage of subjects for the following categories: (1) all TEAEs; (2) Grade 3/4 TEAEs; (3) TEAEs by relationship; (4) TEAEs by maximum severity; (5) TEAEs leading to treatment interruption; (6) TEAEs leading to treatment discontinuation; (7) serious TEAEs; (8) related serious TEAEs; and (9) TEAEs leading to death.

AE summary tables will be presented for TEAEs only and will include the following:

- All TEAEs
- Grade 3/4 TEAEs
- TEAEs by relationship
- TEAEs by maximal severity
- TEAEs leading to treatment interruption
- TEAEs leading to treatment discontinuation
- Serious TEAEs
- Related serious TEAEs
- TEAEs leading to death
- Frequently reported TEAEs

Summaries will be presented by MedDRA SOC and PT using frequency counts and percentages (i.e., number and percentage of subjects with any event). When summarizing the number and percentage of subjects with an event, subjects with multiple occurrences of the same AE or a continuing AE will be counted once, only the maximum severity level will be presented in the severity summaries, and the worst/highest relationship level in the relationship summaries.

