## 12.3.5.2 Clinical Laboratory Assessments

For the laboratory measurements, the raw values and change from baseline of the continuous hematology and chemistry results will be summarized in SI units at each visit of the Current Study Period overall.

The number and percentage of subjects meeting the threshold analysis criterion during the TE Period of the Current Study Period will be summarized based on the 124 Safety Set overall. The threshold analysis criteria will be provided in the SAP.

In addition, a listing containing individual subject hematology and chemistry values outside the reference ranges will be provided. This listing will include data from scheduled and unscheduled visits.

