9 ANALYSIS PERIOD

The analysis periods are described below.

The **Treatment-emergent (TE) Period** will start on or after the first dose date of study drug in Study 124 to 18 days (inclusive) after the last dose date of study drug in Study 124 or up to the last day in Study 124, whichever occurs first.

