10.6.1 Adverse Events

AEs will be classified as pretreatment AEs, treatment-emergent adverse events (TEAEs), or post-treatment AEs, defined as follows:

Pretreatment AE: Any AE that started before the first dose date of study drug in Study 124.

TEAE: Any AE that worsened (either in severity or seriousness) or that was newly developed on or after the first dose date of study drug through the end of the TE Period.

Post-treatment AE: Any AE that increased in severity or was newly developed after the TE Period.

For AEs with missing or partial start dates, if there is no clear evidence that the AEs started before or after study treatment, the AEs will be classified as TEAEs.

Details for imputing missing or partial start dates of AEs are described in Appendix.

TEAE summaries will be presented using number and percentages of subjects for the TE Period based on the Safety Set.

An overview of the TEAE profile will be provided, including total number of TEAEs, with number and percentage of subjects and for the following categories: (1) Any TEAEs; (2) Grade 3/4 TEAEs; (3) TEAEs by Strongest Relationship to the Drug; (4) TEAEs by Maximum Severity; (5) TEAEs Leading to Treatment Interruption; (6) TEAEs Leading to Treatment Discontinuation; (7) Serious TEAEs; (8) Related Serious TEAEs; (9) TEAEs Leading to Death.

AE summary tables will be presented for TEAEs only and will include the following:

- All TEAEs
- Grades 3/4 TEAEs
- TEAEs by Strongest Relationship
- TEAEs by Maximum Severity
- Related TEAEs
- TEAEs Leading to Treatment Interruption
- TEAEs Leading to Treatment Discontinuation
- Serious TEAEs
- Related Serious TEAEs
- TEAEs Leading to Death
- Frequently Reported TEAEs (≥5% at the PT level)

These summaries will be presented by MedDRA SOC and PT using frequency counts and percentages (i.e., number and percentage of subjects with any event) and exposure-adjusted number of events in 100PY. When summarizing the number of events, a subject with multiple events within a category is counted multiple times in that category. When

summarizing the number and percentage of subjects with any event, subjects with multiple occurrences of the same AE or a continuing AE will be counted once, only the maximum severity level will be presented in the severity summaries, and only the strongest relationship level will be presented in the relationship summaries.

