Additional summary table in which the frequency counts and percentages will be presented for TEAEs during the TE period for the following:

- All TEAEs by PT
- Non-Serious TEAEs by SOC and PT
- Related Non-Serious TEAEs by SOC and PT

In addition, listings containing individual subject data for all TEAEs leading to treatment interruption, TEAEs leading to treatment discontinuation, deaths, and serious adverse events (SAEs) will be provided separately for the TE Period. All AEs, including pre- and post-treatment AEs, will be presented in individual subject data listings for the TE Period.

Note that if an event increases in its severity, it will be reported as a separate event in the clinical database and thus may be counted more than once.

Analysis of AEs of Special Interest (AESI):

Three types of AESIs are proposed for Study 124; the Customized MedDRA Queries (CMQ) used may change before database lock.

1. Elevated Transaminases AESI

The AESI of elevated transaminases is defined as AEs whose PTs fall into any of the following categories:

- Alanine aminotransferase abnormal
- Alanine aminotransferase increased
- Aspartate aminotransferase abnormal
- Aspartate aminotransferase increased
- Transaminases abnormal
- Transaminases increased
- Liver function test abnormal
- Liver function test increased
- Hypertransaminasaemia
- Hepatic enzyme increased
- Hepatic enzyme abnormal
- 2. Respiratory Symptom AESI

The AESI of respiratory symptoms is defined as AEs whose PTs fall into any of the following categories:

- Chest discomfort
- Dyspnoea
- Respiration abnormal
- 3. Respiratory Event AESI (including respiratory symptoms or reactive airways)

The AESI of respiratory symptoms or reactive airways is defined as AEs whose PTs fall into any of the following categories:

- Asthma
- Bronchial hyperreactivity
- Bronchospasm
- Chest Discomfort
- Dyspnoea
- Respiration abnormal
- Wheezing

TE AESIs will be summarized using the Safety Set by:

- 1. Number and percentage of subjects by PT
- 2. Number and percentage of subjects by Maximum Severity
- 3. Descriptive summary of duration of events (days)
- 4. Descriptive summary of time-to-onset of the first event (days, relative to first dose date)
- 5. Number and percentage of subjects with exposure-adjusted number of events in 100PY for: (1) TEAEs Leading to Treatment Interruption; (2) TEAEs Leading to Treatment Discontinuation; (3) Serious TEAEs; (4) Related Serious TEAEs; and (5) TEAEs Leading to Death

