10.6.2 Clinical Laboratory

For laboratory measurements, raw values and change from baseline values for the continuous hematology and chemistry results will be summarized in SI units at each visit of the TE Period.

Laboratory tests done in the local laboratory may be used in data analyses if data from the central laboratory are not available.

For hematology and chemistry, the number and percentage of subjects with abnormally low (< lower limit of normal [LLN]) values and with abnormally high (> upper limit of normal [ULN]) values at each visit will be summarized.

The number and percentage of subjects meeting the threshold analysis criterion during the TE Period of the TE Period will be summarized for selected laboratory parameters based on the Safety Set. The threshold analysis criteria are provided in Appendix.

In addition, listings containing individual subject hematology and chemistry values outside of the normal reference ranges will be provided. These listings will include data from both scheduled and unscheduled visits.

LFT elevations meeting ALT or AST > 5xULN, or ALT > 3xULN and total bilirubin > 2xULN, or AST > 3xULN and total bilirubin > 2xULN at one visit during the TE period will also be listed.

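### The SAP states no LUM/IVA-naïve v Rollover breakdown for safety tables, so pooled AESI time-to-onset mixes first exposure with restart and the any-time LFT table pools two draw schedules

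*SAP*

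**What the plan says.** **Pooling.** SAP 10.6.1: "TEAE summaries will be presented using number and percentages of subjects for the TE Period based on the Safety Set". SAP 10.6.2 does the same for laboratory thresholds: "The number and percentage of subjects meeting the threshold analysis criterion during the TE Period of the TE Period" is summarized on the Safety Set, which SAP Section 8 defines as everyone exposed to study drug in Study 124. The protocol is explicit that this is a pooled presentation. Section 12.3.5.1 has "TEAE summaries will be presented using number and percentages of subjects for the Current Study Period based on the 124 Safety Set overall", and Section 12.3.5.2 says the threshold results "will be summarized based on the 124 Safety Set overall".

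**Time origin.** SAP 10.6.1 lists, as item 4 of the AESI summaries, "Descriptive summary of time-to-onset of the first event (days, relative to first dose date", without naming the study. SAP Section 9 says the TE Period "will start on or after the first dose date of study drug in Study 124". The note after Table 11-2 in Appendix A counts study days from the same dose.

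**The cohorts.** Protocol 8.1.1 requires of Rollovers: "Completed the 24-week Treatment Period and the Safety Follow-up Visit in Study 122B". Protocol 8.1.2 excludes those who stopped early in Study 122B, and those with an unexplained interruption-level LFT abnormality at its end. Naïve children did not take part in Study 122B.

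**What is already there.** The SAP separates the cohorts in the visit windows (Tables 11-1 and 11-2), the sweat chloride baseline rule and the programmable deviation rules. The 5% cut applies only to the frequently reported TEAE table. There are also uncut tables, including "All TEAEs by PT", and all AEs are listed by subject.

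**The concern.** Long-term safety is the primary objective, and the pooled tables answer it for the study as a whole. They cannot show whether an AESI followed the start of LUM/IVA or its resumption in a child who had already completed a Treatment Period on it. Timing matters most for the respiratory AESIs, because Protocol 9.5 describes an initial transient fall in lung function on dosing, seen in healthy subjects. A pooled median onset in days would be read naturally as onset after starting treatment, and for Rollovers it is not that.

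The LFT threshold table counts children who met a criterion at any time in the TE Period. Naïve children are tested more often in the first 24 weeks. Part of the pooled percentage therefore reflects testing frequency, weighted by a cohort split that the documents do not give.

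**Working it through.** The plan has no power or sample-size calculation to reproduce; about 50 children are enrolled at a regulator's request. The check covers the time origin, the draw schedules and the precision of split columns.

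**1. Time origin.** Suppose item 4 counts from the first Study 124 dose.
- Naïve child, event on study day 15: day 15 since first exposure.
- Rollover, same study day: 24 × 7 = 168 days of Study 122B treatment come first, so about 168 + 15 = day 183 since first exposure. Any off-drug gap adds to this. The documents do not state its length; an assumed 14 days would make the shift 168 + 14 = 182 days.

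If the first-ever dose were meant instead, Rollover onsets in Study 124 could not fall below about 168 days, and the pooled distribution would still be a mixture.

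**2. Scheduled LFT draws** after Day 1, from Protocol Tables 3-1 and 3-2, counting full chemistry as including LFTs (Table 11-1). The Safety Follow-up draw is left out; both schedules contain it.
- Naïve: days 15, 29, 57, 85, 113, 169, then 253, 337, 421, 505, 589, 673 = 12.
- Rollover: days 15, 85, 169, then the same six later days = 9.

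**3. Chance that a scheduled draw catches an elevation**, over the 672 days from Day 1 to Day 673. Assumptions: equal risk in both cohorts, one elevation lasting d days, onset uniform over the period, draws on target days, no unscheduled draws. An elevation is caught if its onset falls within d days before a draw, so

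P(caught) = Σ min(gap, d) / 672, summed over the gaps between successive draws.

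Gaps in days: naïve 14, 14, 28, 28, 28, 56, then 6 × 84; Rollover 14, 70, 84, then 6 × 84. Each set sums to 672.

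| Duration d (days) | Naïve | Rollover | Ratio |
|---|---|---|---|
| 14 | 168/672 = 25.0% | 126/672 = 18.75% | 1.33 |
| 28 | 308/672 = 45.8% | 238/672 = 35.4% | 1.29 |
| 56 | 504/672 = 75.0% | 462/672 = 68.75% | 1.09 |
| 84 | 100% | 100% | 1.00 |

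**4. Effect on the pooled figure.** Assume a true risk of 10% and 28-day elevations.
- Rollover share 30%: 10% × (0.3 × 0.354 + 0.7 × 0.458) = 4.3%.
- Rollover share 90%: 10% × (0.9 × 0.354 + 0.1 × 0.458) = 3.6%.
- With 25 children per cohort (assumed), expected detections are 25 × 0.10 × 0.458 = 1.15 naïve and 25 × 0.10 × 0.354 = 0.89 Rollover, a difference of about a quarter of one child.

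**5. Precision of split columns.** With zero events the two-sided 95% exact upper limit is 1 − 0.025^(1/n): 30.8% at n=10, 16.8% at n=20, 11.6% at n=30 and 7.1% at n=50. The cohort sizes are assumed.

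**The case against.** The best defence is that pooling is prespecified and fits the objective. The target population is children aged 12 to <24 months when treatment begins, which covers both cohorts. The study is descriptive, has about 50 children and tests no hypothesis. That stands: the pooled percentages are legitimate Study 124 incidences.

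The time origin is also less open than item 4 alone suggests. The TE Period, the study-day note and the pretreatment AE definition all use the first Study 124 dose, so naming it is a clarification. It does not remove the mixture.

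On LFTs, the calculation ignores unscheduled draws. Protocol 11.4.3 requires repeat testing for symptomatic elevations and weekly tests for four weeks after resumption. Protocol 11.4.2 allows additional evaluations, and SAP 10.1 uses unscheduled values in deriving extremes. This stands and would narrow the difference.

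Split columns do not equalize the schedules, and small columns invite a naïve-v-Rollover comparison confounded by schedule and by selection of Study 122B completers. This is a fair warning, and the reason for a footnote. Subject listings and cohort-specific visit windows already allow some separation, but a reader of the summary tables alone cannot recover the cohorts.

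Finally, table shells are not in the documents. The defensible statement is that no cohort column is stated, not that none will be produced.

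**Conclusion.** The point holds as a low-cost improvement. Time-to-onset is the stronger half: on the SAP's own definitions, a pooled summary combines clocks at least about 168 days apart and cannot describe onset after starting LUM/IVA. The LFT half is modest. The schedule alone gives a detection ratio of 1.0 to about 1.33 over 96 weeks, on the assumptions of equal risk, uniform onset, on-target visits and no unscheduled draws.

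Four stronger readings are not supported:
- *A twofold LFT detection difference.* A reader might infer this from the 6 v 3 scheduled draws through Week 24. No any-time table ending at Week 24 is planned, so that contrast describes no output.
- *Hidden events or invalid pooled percentages.* The uncut TEAE tables and the listings show every event.
- *A known direction of distortion.* Rollovers exclude early stoppers, but Protocol 8.1.1 and 11.4.3 admit some after an interruption or an incomplete rechallenge following raised transaminases. The cohort split and event timing are not given either.
- *A need to split every SOC/PT table.* The problem lies in a few outputs.

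**What to change.** - In SAP 10.6.1, AESI item 4, state that time-to-onset is relative to the first dose date in Study 124.
- Present the AESI tables (including time-to-onset), the TEAE overview and the LFT threshold table in LUM/IVA-naïve, Rollover and Total columns, with Total as the main summary. Splitting the SOC/PT tables is optional.
- Base any statement about onset after starting treatment on the naïve column.
- Footnote the LFT table with the scheduled draws through Week 96 (12 naïve, 9 Rollover, excluding Safety Follow-up), and say that the columns are descriptive and not a comparison.

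The cost is SAP wording and two extra columns in a few tables, from data already held. Protocol 12.3 lets the SAP define additional analyses, and the Total column preserves the protocol's overall presentation and its precision. The downside is wide uncertainty in the small columns, as shown under the check.

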#### 12.3.1 General Considerations

All individual subject data will be presented in data listings based on the 124 All Subjects Set.

Continuous variables will be summarized using the following descriptive summary statistics: number of subjects, mean, SD, SE, median, minimum value (min), and maximum value (max).

Categorical variables will be summarized using counts and percentages.

**Baseline value** will be defined as the most recent non-missing measurement (scheduled or unscheduled) collected on or before the first dose of LUM/IVA in Study 124.

For sweat chloride, values at each visit will be based on averaged measurements from left and right arms as specified in Section 11.2.1. For Rollover Subjects, baseline will be defined as the most recent non-missing measurement (scheduled or unscheduled) collected on or before the first dose of LUM/IVA in Study 124. For LUM/IVA-naïve Subjects, baseline will be defined as the average of the values at screening and the pretreatment measurement on Day 1 of Study 124. If only 1 pre-first dose measurement of sweat chloride is available, that measurement will be considered the baseline.

Change (Absolute Change) from baseline will be calculated as postbaseline value – baseline value.

**Current Study Period** starts from the first dose of study drug in Study 124 to the last day in Study 124.

The Treatment-emergent (TE) Period for the Current Study Period starts on or after the first dose date of study drug in Study 124 to 14 days (inclusive) after the last dose of study drug in Study 124 or up to the last day in Study 124, whichever occurs first.

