In addition, listings containing individual subject data for all TEAEs leading to treatment interruption, TEAEs leading to treatment discontinuation, deaths, and serious adverse events (SAEs) will be provided separately. All AEs, including pre- and post-treatment AEs, will be presented in individual subject data listings.

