## 13.1.2.2 Reporting and Documentation of Serious Adverse Events

All SAEs that occur after obtaining informed consent and assent (where applicable) through the Safety Follow-up Visit, regardless of causality, will be reported by the investigator to Vertex Global Patient Safety (GPS) within 24 hours of identification. In addition, all SAEs that occur after the Safety Follow-up Visit and are considered related to study drug(s) will be reported to Vertex GPS within 24 hours of identification.

For SAEs that occur after obtaining informed consent and assent (where applicable) through the Safety Follow-up Visit, the SAE Form will be completed for new/initial events as well as to report follow-up information on previously reported events. Investigators are asked to report follow-up information as soon as it becomes available to ensure timely reporting to health authorities.

Please send completed SAE Forms to Vertex GPS via:

Email: [contact] (preferred choice)

[contact]

For technical issues related to submitting the form, contact [contact]

SAEs that occur after the Safety Follow-up Visit and are considered related to study drug(s) will be recorded on the Vertex Clinical Trial Safety Information Collection Form (hereafter referred to as the "SAE Form") using a recognized medical term or diagnosis that accurately reflects the event. SAEs will be assessed by the investigator for relationship to the investigational study drug(s) and possible etiologies. On the SAE Form, relationship to study drug(s) will be assessed only as related (includes possibly related) or not related (includes unlikely related), and severity assessment will not be required. For the purposes of study analysis, if the event has not resolved at the end of the study reporting period, it will be documented as ongoing. For purposes of regulatory safety monitoring, the investigator is required to follow the event to resolution and report the outcome to Vertex using the SAE Form.

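### SAP 10.6.1 limits the death, SAE and all-AE listings to the TE Period, a limit the protocol does not set; it conflicts with the SAP's own AE definitions and should be removed

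*SAP*

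**What the plan says.** Protocol 12.3.5.1 asks for separate listings, ending with "TEAEs leading to treatment discontinuation, deaths, and serious adverse events (SAEs) will be provided separately". It then says "All AEs, including pre- and post-treatment AEs, will be presented in individual subject data listings". Neither sentence names a period.

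SAP 10.6.1 carries both sentences over and adds a period to each: "deaths, and serious adverse events (SAEs) will be provided separately for the TE Period" and "All AEs, including pre- and post-treatment AEs, will be presented in individual subject data listings for the TE Period".

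SAP 9 defines only one analysis period, the TE Period. It runs from the first dose in Study 124 to "18 days (inclusive) after the last dose date of study drug in Study 124", or to the last day in the study if that is earlier. SAP 10.6.1 defines a post-treatment AE as "Any AE that increased in severity or was newly developed after the TE Period" and a pretreatment AE as one that began before the first dose.

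In both documents the AE summary tables are restricted to TEAEs. SAP 3.1 describes its changes to the protocol as typographical and administrative only.

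**The concern.** Safety is the primary endpoint, and the study keeps looking for harm after the drug is stopped. Ocular AEs are collected at the Follow-up OE (Tables 3-1 and 3-2; protocol 13.1.1.3). Protocol 13.1.2.2 adds that "all SAEs that occur after the Safety Follow-up Visit and are considered related to study drug(s) will be reported". These events fall after the TE Period, so the TEAE tables cannot show them and a listing is the only AE output that can.

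A programmer who follows SAP 10.6.1 to the letter would filter the death and SAE listings at the end of the TE Period. For the all-AE listing the same programmer has an instruction that cannot be carried out. In a study of about 50 children, one late death, related SAE or lens event would matter to a reader of the report, and it could be missing from the listing where that reader would look first.

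**Working it through.** The plan gives no figure on this point and nothing in it is powered. The check compares the texts and then counts days.

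**Texts side by side**

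| Item | Protocol 12.3.5.1 | SAP 10.6.1 |
|---|---|---|
| Death and SAE listings | No period limit | Limited to the TE Period |
| All-AE listing | No period limit; pre- and post-treatment AEs included | Limited to the TE Period; pre- and post-treatment AEs still included |
| AE tables | TEAEs only | TEAEs only |

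The first row is a plain restriction. The second is a contradiction: a post-treatment AE starts or worsens after the TE Period and a pretreatment AE starts before it, so neither belongs to that period. The third row is unchanged from the protocol.

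**Day count** (days after the last dose)

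1. End of the TE Period (SAP 9): day 18, or the last study day if earlier.
2. Safety Follow-up Visit (protocol 9.1.3): 2 weeks ± 4 days, so 14 − 4 = 10 to 14 + 4 = 18. Every AE up to an in-window visit lies inside the SAP's TE Period and is both tabulated and listed.
3. Children without a Safety Follow-up Visit (protocol 13.1.1.3): general AE collection ends no later than day 14, which is before day 18. Nothing is lost here either.
4. Follow-up OE (protocol 9.1.3): 24 weeks ± 14 days. 24 × 7 = 168, so 168 − 14 = 154 to 168 + 14 = 182. This is 154 − 18 = 136 to 182 − 18 = 164 days after the TE Period has ended. An ocular AE first noted there is always a post-treatment AE.
5. Related SAEs reported after an in-window Safety Follow-up Visit: the visit is on day 18 at the latest, so any such event that starts after day 18 is outside the TE Period.

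The result does not depend on which TE definition is used. The protocol's own end point, "14 days (inclusive) after the last dose of study drug in Study 124", would bring the cut forward by 18 − 14 = 4 days and put the Follow-up OE 140 to 168 days beyond it.

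**Before the first dose.** The TE Period starts at the first dose. Read literally, the limit also removes AEs and SAEs between consent and the first dose. Enrolled children who were never dosed have no TE Period, although SAP 10.6 bases all listings on the All Subjects Set, which includes them.

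**The case against.** The best defence is that this is a drafting slip and that other text covers the gap. Much of that defence stands.

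- A reader might infer that late events appear in no AE listing at all. The documents do not establish this. The all-AE sentence expressly names post-treatment AEs, SAP 10.1 says all individual subject data will be listed, and no rule says which instruction prevails. What can be shown is an explicit limit on the death and SAE listings and a contradiction in the all-AE listing.
- A reader might infer that everything after a child stops the drug is lost. That is too broad, because events up to day 18 are TEAEs.
- A reader might call the absence of late events from the tables a departure from the protocol. It is not, since the protocol restricts its AE tables in the same way.
- A reader might measure the loss by the share of post-dose calendar time outside the TE Period. That would mislead. General AE collection ends at the Safety Follow-up Visit or by day 14, and after that the schedules call for ocular AEs only. Early discontinuers are asked to stay to Week 96 (protocol 9.1.4) and parents are asked about AEs at each visit (13.1.1.3), so some further events may be recorded, but time off drug does not measure them.
- OE findings are listed without a period limit (SAP 10.6.7), so a lens finding would be reported, though SAP 10.6.7 does not promise the severity, causality and outcome held in an AE record. Children who discontinue the study are listed with reasons (SAP 10.2.1). The protocol, however, counts the study as completed at the Safety Follow-up Visit (12.3.2.1), so a later death might not appear there.

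There are signs of a mechanical edit. SAP 10.6.2, 10.6.3, 10.6.4 and 10.6.6 name the TE Period twice in one phrase, where the protocol names the TE Period within its Current Study Period. That is an inference: the two listing sentences in protocol 12.3.5.1 do not mention the Current Study Period. A slip still has to be corrected, because the programmer works from the written instruction.

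**Conclusion.** The point holds as a wording error with a limited but real consequence. SAP 10.6.1 adds an undeclared limit to two listing sentences. Taken as written, it removes from the dedicated death and SAE listings every event more than 18 days after the last dose, and it makes the all-AE sentence impossible to follow.

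The events realistically at risk are ocular AEs at the Follow-up OE and deaths or related SAEs after the Safety Follow-up Visit. Their number cannot be estimated from the documents and is probably small. The conclusion rests on reading the SAP sentences literally and on visits falling in their windows. It does not assume that the sponsor meant to exclude these events. The correction should be made before the listings are programmed.

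**What to change.** In SAP 10.6.1:

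1. Remove the TE Period limit from the death and SAE listings and from the all-AE listing. State that they cover every AE, SAE and death collected from consent to the last day in Study 124.
2. Flag each record as pretreatment, treatment-emergent or post-treatment, and show days since the last dose.
3. Keep the TE limit for the listings of TEAEs leading to interruption or discontinuation and for all TEAE tables.
4. Confirm that related SAEs reported after the Safety Follow-up Visit reach the listing dataset. Protocol 13.1.2.2 sends them to the sponsor's safety group on the SAE Form and does not show that they enter the clinical database.

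The cost is a short SAP amendment, a flag and one derived column, plus one check of data flow. No table changes and no new data are collected. If the check in item 4 fails, those late SAEs will also have to be reconciled from the safety database.
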